#### **4.1.3 ALS Reversals**

To look for an increase in the frequency of ALS reversals, we will count the number of participants who have an ALSFRS-R score that improves by 4 points or more over 6 months. The observed frequency of spontaneous ALS reversals defined in this way is 2-5% (30). We will look for an increase in this frequency to at least 10% (1 in 10).

#### **4.1.4 Enrollment**

To determine whether the participant enrollment rate in this study is greater than in studies with more traditional designs, we will compare our enrollment rate (participants enrolled per month) to the mean ALS trial enrollment rate of 2 (4) using a chi-squared test.

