### 1.2 Secondary Hypotheses

Secondary hypotheses are as follows:

1. Theracurmin can increase the frequency of ALS reversals (defined by an improvement of 4 or more points in the ALSFRS-R over the course of 6 months) from 2-5% (observed spontaneously) to at least 10%.
2. Theracurmin can alter the fecal microbiome in patients with ALS.
3. The fecal microbiome of patients with ALS is significantly different from matched control subjects.
4. The fecal microbiome of patients with ALS is significantly different between subgroups with differing clinical features including sporadic vs. familial, anatomical location of symptom onset, and rate of progression as measured on the ASLFRS-R.
5. The novel features of this pilot trial will be associated with improved participant enrollment compared to prior more traditional ALS trials where enrollment is 2 participants per site per month.
6. The novel features of this pilot trial will be associated with improved participant retention compared to prior more traditional ALS trials where the dropout rate is 22% at 12 months.
7. The novel features of this pilot trial will be associated with improved participant compliance compared to prior more traditional ALS trials.

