### **3 DESIGN & PROCEDURES:**

#### **3.1 Design Overview**

This will be a 6-month, widely inclusive, largely remote/virtual, single-center, open-label pilot trial utilizing a historical control group. Following informed consent and screening, participants will take the intervention (see section 3.2.1) for 6-months. Treatment with the intervention Theracurmin HP and all study outcome measures and labs are being performed exclusively for research purposes. Collected data includes ALSFRS-R, fecal sample microbiome sampling, adverse events, and concomitant medications. Participants will be asked to register for an account on PLM with the help of the study coordinator. User IDs associated with their PLM account will be recorded by the study coordinator and shared with study staff at PLM. When registering, participants will have the opportunity to review PLM's terms and conditions (Appendix A) as well as their privacy policy (Appendix B). After the baseline video/telephone visit, participants will be asked to enter the following data: weight and height, Theracurmin treatment evaluations (Appendix C), ALSFRS-R score (Appendix D) and Thrive Questionnaires (Appendix E). Participants will be given the following study documents and materials shipped to their home:

A PLM bag (Appendix F) including:

1. Welcome letter (Appendix G)
2. Study One-Sheet (Appendix H)
3. Study drug
4. Microbiome kits
5. PatientsLikeMe gifts

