### **3.3.5 Enrollment Rate**

Enrollment rate will be calculated as the number of participants enrolled per month. A previous meta-analysis showed the mean ALS trial enrollment rate to be 2.2 participants per site per month (4). Our previous Lunasin trial had an enrollment rate of 9 participants per site per month (6).

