## 3.5 Participants

Primary participants will be patients with ALS (PALS) who are cared for by [name], or who contact our site inquiring about this study. 50 participants will be enrolled.

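### The chi-squared test in Section 4.1.4 is given a monthly rate where it needs counts, so it could miss a real enrollment gain; and a gain at one center could not be credited to the design

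*Combined protocol and SAP*

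**What the plan says.** Section 1.2 (hypothesis 5) of the combined protocol and SAP states: "The novel features of this pilot trial will be associated with improved participant enrollment". The comparator there is "prior more traditional ALS trials where enrollment is 2 participants per site per month". Section 3.3.5 defines the outcome: "Enrollment rate will be calculated as the number of participants enrolled per month". Section 4.1.4 gives the analysis: "we will compare our enrollment rate (participants enrolled per month) to the mean ALS trial enrollment rate of 2 (4) using a chi-squared test".

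Section 3.3.5 cites the same source as Section 4.1.4 but gives the "mean ALS trial enrollment rate to be 2.2 participants per site per month". It adds, for the team's own earlier hybrid-virtual trial: "Our previous Lunasin trial had an enrollment rate of 9 participants per site per month" (9.1 in Section 2.3).

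Section 3.5 fixes the number: "50 participants will be enrolled". Section 3.1 describes a "largely remote/virtual, single-center, open-label pilot trial utilizing a historical control group".

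For this test, no section gives observed and expected counts, the start and end of the enrollment period, a significance level, a sidedness, or the spread of the benchmark.

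**The concern.** A one-sample chi-squared test compares an observed count with an expected count, and its power comes from the size of those counts. Section 4.1.4 names two rates instead. If they go straight into the formula, 50 enrollments carry no more weight than a single month's intake, and a center enrolling at twice the benchmark would be reported as not significantly faster.

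A second matter would remain even with the right test. The comparator is a mean over earlier trials and sites, and this trial has one center. The documents give no enrollment rate for a traditionally designed trial at this center, so a rate above the benchmark cannot be divided between the design and the site. Hypothesis 5 nevertheless ties the improvement to the trial's new features.

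At stake is the conclusion on one secondary feasibility hypothesis. Neither the primary analysis nor safety is affected.

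**Working it through.** The plan gives no critical value, power or pass mark for this test, so there is no figure to reproduce.

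**Inputs**
- Enrolled: 50 primary participants (Section 3.5), one center (Section 3.1).
- Benchmark: 2 per month (Sections 1.2 and 4.1.4) or 2.2 (Section 3.3.5).
- Earlier trial by the same team: 9.1 per month (Section 2.3).
- Level: two-sided 5%, critical value 3.84 on 1 df. This is an assumption; Section 4.1.2 sets a one-tailed 5% level for the primary hypothesis only.
- T is the number of months taken to enroll 50, and r = 50/T.

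**1. The test as written.** With rates as observed and expected values, X² = (r − 2)²/2. It passes when r > 2 + √(3.84 × 2) = 2 + 2.77 = 4.77 per month, that is, 50 enrolled within 50/4.77 = 10.5 months.

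**2. The same test on counts.** Observed 50, expected 2T:

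X² = (50 − 2T)²/(2T) = T × (r − 2)²/2.

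The written statistic is therefore too small by a factor T, the number of months of enrollment. This is the sense in which it treats the data as one month of observation.

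Example at r = 4 per month (T = 12.5):
- as written: (4 − 2)²/2 = 2.0, p = 0.16;
- on counts: (50 − 25)²/25 = 25, p < 0.000001.

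**3. Exact analysis.** With 50 fixed and enrollment treated as a Poisson process of rate λ, 2Tλ follows a chi-squared distribution with 100 df, whose 2.5% and 97.5% points are 74.22 and 129.56. The exact 95% confidence interval for λ is 74.22/(2T) to 129.56/(2T). The lower limit exceeds 2 when T < 74.22/4 = 18.6 months, that is, from 50/18.555 = 2.69 per month. In the example (T = 12.5) the interval is 74.22/25 to 129.56/25, or 2.97 to 5.18 per month, clear of 2.

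**4. Pass marks at matching error levels (participants per month)**

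| Benchmark and level | As written | Exact, 50 enrolled |
|---|---|---|
| 2, two-sided 5% | 4.77 | 2.69 (T ≤ 18.6) |
| 2, one-sided 5% | 4.33 | 2.57 (T ≤ 19.5) |
| 2.2, two-sided 5% | 5.11 | 2.96 (T ≤ 16.9) |

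**5. Effect of 2 versus 2.2.** At 5 per month, the written test gives (5 − 2)²/2 = 4.5 (p = 0.034) against 2, and (5 − 2.2)²/2.2 = 3.56 (p = 0.059) against 2.2. The choice of benchmark can reverse the result.

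**6. At the earlier trial's rate.** For r = 9.1, the written statistic is 7.1²/2 = 25.2. On counts, T = 50/9.1 = 5.49 months and 10.99 are expected, giving X² = 138. Both reject.

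**7. Site variation (assumption only).** The documents give no between-site spread. If traditional-design site rates followed a gamma distribution with mean 2 and a coefficient of variation of 0.25, 0.5 or 1.0, one such site would beat the benchmark of 2 by the count-based test in about 15%, 24% or 27% of cases, against 3.4% with no site variation. This shows the direction of the problem, not its size here.

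**The case against.** The strongest reply is that the sponsor means the ordinary count version: 50 observed against 2 × months. That reading is possible, does not depend on the time unit, and passes from 2.64 per month, close to the exact result. But no section states it, and Sections 3.3.5 and 4.1.4 both name the rate. The point stands as a correction to the text.

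Three stronger readings are tempting and are not supported.

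- A reader might infer that the result turns on whether the analyst works in weeks, months or years. The formula does scale with the unit, which shows that it is ill-formed, but Sections 3.3.5 and 4.1.4 both fix the unit as a month.
- A reader might infer that the test ignores how long enrollment took. It does not: T enters through r = 50/T. What is lost is the weight of 50 events, which is a loss of precision.
- A reader might infer that site volume explains fast enrollment as well as the design does. The documents give no site volume and no between-site spread, so that cannot be said. Sections 3.5 and 3.6 also admit people who contact the center and provide for website and Twitter notices, so recruitment is not confined to the center's own clinic. Only the weaker statement holds: the two explanations cannot be separated.

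It is also fair to say that hypothesis 5 speaks of association, in a pilot, and that 2 may be 2.2 rounded. Neither removes the need for modest wording and a single benchmark.

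**Conclusion.** The concern holds in limited form. Section 4.1.4 applies a test for counts to a rate. Taken as written, it needs more than 4.77 per month to pass, where an exact analysis of the same 50 enrollments needs 2.69, both at two-sided 5% against 2. It could miss a real gain between about 2.7 and 4.8 per month. The error runs in one direction only: for any enrollment period longer than a month the written statistic is smaller than the count-based one, so it creates no false success. If enrollment again ran near 9.1 per month, the choice of test would not matter.

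Separately, no choice of test lets this comparison credit a gain to the design, and that limit applies however fast enrollment proves to be.

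These results assume a 5% level, Poisson enrollment at a constant rate, and a benchmark treated as known without error. The last assumption is generous to the trial, since the benchmark is itself a mean whose spread is not given.

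**What to change.** - **Section 4.1.4:** replace the chi-squared test with the number of primary participants enrolled (50) over T months, from opening of enrollment to the last enrollment. Do not count the household controls of Section 3.5.3. Report 50/T with an exact 95% confidence interval, using 2Tλ ~ chi-squared with 100 df, and compare the lower limit with one stated benchmark.
- **Sections 1.2, 3.3.5 and 4.1.4:** reconcile 2 with 2.2 before enrollment data are examined. Using 2.2 moves the pass mark from 2.69 to 2.96 per month.
- **Section 1.2, hypothesis 5:** word it as a descriptive comparison with a published mean, and do not credit any gain to the trial's new features. The center's own rates from traditionally designed ALS trials may be listed as context if available, but not as a decision rule: they are not in the documents and may differ in eligibility and era.

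The cost is SAP wording and a more modest conclusion for a secondary feasibility hypothesis. The only added data need is the opening date and the date of the last enrollment.

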### 2.3 Success of Previous Hybrid Virtual/Remote Trial

We previously conducted an open-label, single-center, hybrid-virtual 12-month trial of Lunasin for patients with ALS (6). This single-center trial featured broad inclusion criteria, historical controls, mostly virtual data collection, and real-time results. Participants measured their ALSFRS-R score, weight and perceived efficacy, and recorded these monthly on PatientsLikeMe (PLM; an online platform described section 2.7). ALSFRS-R decline was compared to historical controls. For each enrolled participant, PLM identified 3 historical controls matched according to pre-treatment ALSFRS-R progression, as in their previous Lithium study (7). We had 90% power to detect 50% slowing in decline of ALSFRS-R scores.

Although there were no significant differences in ALSFRS-R ( $p=0.99$ ) between study participants and historical controls, the study's outcomes suggested that there is utility and internal validity in a virtual trial model. Enrollment rate was 9.1 participants per site per month, which is the fastest rate of any ALS trial in history. As in most ALS trials, our 50 participants were primarily white (94%) males (58%), mean age of 60, limb onset disease (82%), taking riluzole (60%). However, our participants had longer disease duration than those in most trials, and several had non-invasive ventilation, PEG and/or tracheostomy, which are traditional exclusion criteria. This trial population was therefore more representative of the population seen in ALS clinics. In spite of enrolling patients with longer and more advanced disease, the survivor retention rate was 84%, while the survivor retention rate in traditional ALS trials is 78% (5).

We also looked at the accuracy of patient recorded ALSFRS-R and weight measurements. Lin's concordance (C) showed high agreement between coordinator and participant derived ALSFRS-R and weight respectively at month 1 ( $C=0.9939, 0.9947$ ) and month 12 visits ( $C=0.9428, 0.9905$ ). These results suggest that participant recorded ALSFRS-R scores and weight are sufficiently accurate to be used in a clinical trial.

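### The enrollment-rate test takes 2 per month as its benchmark, while the outcome section gives 2.2 from the same reference: a minor inconsistency in the lenient direction

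*Combined protocol and SAP*

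**What the plan says.** Three sections of the combined protocol and SAP give the benchmark enrollment rate of traditional ALS trials.

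- Section 1.2 (Secondary Hypotheses, item 5) sets the comparison against earlier trials "where enrollment is 2 participants per site per month".
- Section 3.3.5 (Enrollment Rate), citing reference (4): "A previous meta-analysis showed the mean ALS trial enrollment rate to be 2.2 participants per site per month".
- Section 4.1.4 (Enrollment) compares the observed monthly rate "to the mean ALS trial enrollment rate of 2 (4) using a chi-squared test".

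Sections 3.3.5 and 4.1.4 cite the same reference for the same quantity. Section 3.1 describes a single-center trial, so a rate per month and a rate per site per month are the same thing here.

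Section 4.1.4 gives no alpha, sidedness or expected count for the test.

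**The concern.** The figure in section 4.1.4 is the null value of a named test of a listed secondary hypothesis, so it sets how fast enrollment must be before the trial is called faster than traditional trials. The protocol carries two values for it. The hypothesis and its test both use the lower one, which is easier to beat.

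A trial that enrolled exactly at the unrounded historical mean could therefore be reported as an improvement more often than it would be if tested against that mean. What is at stake is one feasibility claim about the virtual design. Neither the primary analysis nor the sample size depends on it.

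**Working it through.** **Inputs**

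- Benchmark λ0: 2 per month (sections 1.2 and 4.1.4) or 2.2 (section 3.3.5).
- Number enrolled: section 3.5 says "50 participants will be enrolled". N is taken as fixed at 50, with T the months needed to enroll them.
- Earlier virtual trial (section 2.3): "Enrollment rate was 9.1 participants per site per month".
- Alpha: 5%, an assumption. Section 4.1.2 gives 5% and a one-tailed comparison for the primary hypothesis only, so one- and two-sided results are both shown.
- Enrollment is modelled as a Poisson process with a constant rate, also an assumption.

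The plan states no critical value or power for this test, so there is no computed figure to reproduce. The one check on the stated 2 is rounding: 2.2 to the nearest whole number is 2.

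**Step 1. Cut-offs**

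*Exact test.* With N = 50 fixed, 2 × λ0 × T follows a chi-squared distribution on 100 degrees of freedom under the null. Enrollment is declared faster when T falls below q / (2 × λ0), where q is the lower 5% point (77.93), or the lower 2.5% point (74.22) for the upper tail of a two-sided test.

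- One-sided, λ0 = 2: 77.93 / 4 = 19.48 months, a rate of 50 / 19.48 = 2.57 per month.
- One-sided, λ0 = 2.2: 77.93 / 4.4 = 17.71 months, or 2.82 per month.
- Two-sided, λ0 = 2: 74.22 / 4 = 18.56 months, or 2.69 per month.
- Two-sided, λ0 = 2.2: 74.22 / 4.4 = 16.87 months, or 2.96 per month.

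*Count-based chi-squared.* The statistic is (50 − E)² / E on 1 degree of freedom, with E = λ0 × T. It reaches 3.84 when E = 37.93.

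- λ0 = 2: T = 37.93 / 2 = 18.96 months, or 2.64 per month.
- λ0 = 2.2: T = 37.93 / 2.2 = 17.24 months, or 2.90 per month.

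**Step 2. Chance of declaring faster enrollment when the true rate is 2.2 per month**

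This is P(chi-squared on 100 df < 2 × 2.2 × cut-off T). For the exact one-sided test against 2, the argument is 4.4 × 19.48 = 85.7, and the probability is 15.5%.

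| Test, assumed alpha 5% | Benchmark 2 | Benchmark 2.2 | Observed rates where the verdict differs |
|---|---|---|---|
| Exact, one-sided | 15.5% | 5.0% | 2.57 to 2.82 per month |
| Exact, upper tail of two-sided | 9.0% | 2.5% | 2.69 to 2.96 per month |
| Count-based chi-squared, upper tail of two-sided | 11.6% | 3.4% | 2.64 to 2.90 per month |

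The rows differ in sidedness and should be compared across, not down. The 3.4% exceeds 2.5% because the chi-squared test is a large-sample approximation; the benchmark plays no part in that.

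**Step 3. Effect at plausible rates**

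- At a true rate of 3 per month, the exact one-sided test declares faster enrollment 88% of the time against 2 and 68% against 2.2.
- At 4 per month the figures are 99.97% and 99.6%.
- At an observed 9.1 per month, T = 50 / 9.1 = 5.49 months. E is 10.99 (null 2) or 12.09 (null 2.2), and chi-squared is 138.5 or 118.9. Both p-values are below 1e-26.

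**The case against.** The strongest reply is that this is rounding and nothing more. The protocol rounds a similar figure elsewhere: section 2.3 gives the earlier trial's rate as 9.1, and section 3.3.5 says "Our previous Lunasin trial had an enrollment rate of 9 participants per site per month (6". The hypothesis in section 1.2 and its test in section 4.1.4 agree with each other at 2; only the descriptive outcome text carries the decimal. With enrollment near 9 per month, nobody's conclusion would change.

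Most of this stands. Rounding is the likely origin, and the practical effect is small. It does not justify leaving a rounded null value in a test when the more precise figure is already in the protocol and the rounding favours the hypothesis.

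Two stronger readings are tempting, and the documents do not support them.

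- A reader might infer that the test has an inflated type I error. It does not for the null it names: an exact test of a rate of 2 at 5% rejects 5% of the time when the rate is 2. The 15.5%, 9.0% and 11.6% are rejection probabilities at a different rate, 2.2. They describe a lenient benchmark.
- A reader might infer that a chi-squared test is simply the wrong method. Comparing an observed count with an expected count (rate times months) by chi-squared is workable. What section 4.1.4 lacks is a statement of the expected count, alpha and sidedness. An exact Poisson test is a refinement.

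**Conclusion.** The inconsistency is real: 2 in sections 1.2 and 4.1.4 against 2.2 in section 3.3.5, with the last two citing the same reference. The value used in the test is the more lenient one. If the true rate were 2.2 per month, using 2 would roughly triple the chance of declaring faster enrollment, whichever of the three test forms is meant.

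The point is nonetheless minor. The benchmark decides the outcome only in a band about 0.25 per month wide, just under 3 per month. The only precedent the documents give for this design is about three times that.

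These figures assume alpha 5%, exactly 50 enrolled and a constant enrollment rate, and they treat the benchmark as known without error. That 2.2 is the unrounded source value is an inference from section 3.3.5; the cited reference was not available to check. The documents do not support a conclusion that the enrollment comparison is invalid or that its likely result is in doubt.

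**What to change.** Use 2.2 participants per site per month in sections 1.2 and 4.1.4, after confirming it against reference (4), so that all three sections agree.

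In section 4.1.4, define the comparison as the 50 enrolled against 2.2 × T expected, where T is the months of enrollment. Use a count-based chi-squared test or, preferably, an exact one-sample Poisson test. State alpha and sidedness, and report the observed rate with its exact 95% confidence interval.

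The cost is a change of wording. No new data and no change in sample size or conduct are needed. The downside is a slightly less favourable threshold: on the exact one-sided test, the rate needed rises from 2.57 to 2.82 per month.

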#### **4.1.5 Retention**

To determine whether participant retention in this study is greater than in studies with more traditional designs we will compare our dropout rate (percentage of living enrolled participants that complete the Month 6 Visit) to the mean ALS participant dropout rate of 22% at 12 months (5) using a chi-squared test.

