### **3.3.6 Retention**

Retention will be assessed by looking at the dropout rate at 6 months (the percentage of surviving enrolled patients who complete the Month 6 Visit). A previous meta-analysis of traditional clinical trials showed the mean ALS participant dropout rate to be 22% at 12 months (5). Our previous virtual trial with Lunasin had a dropout rate of 16% at 12 months (6).

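### Sections 3.3.6 and 4.1.5 define the dropout rate as the percentage who complete Month 6, then compare it with a 22% dropout benchmark: an inverted definition of one secondary feasibility endpoint

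*Combined protocol and SAP*

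**What the plan says.** Secondary Hypothesis 6 (section 1.2) expects "improved participant retention compared to prior more traditional ALS trials where the dropout rate is 22% at 12 months".

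Two sections turn this into an endpoint and a test:

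- Section 3.3.6 (outcome measure) assesses retention through "the dropout rate at 6 months (the percentage of surviving enrolled patients who complete the Month 6 Visit").
- Section 4.1.5 (analysis) takes "our dropout rate (percentage of living enrolled participants that complete the Month 6 Visit") and compares it with "the mean ALS participant dropout rate of 22% at 12 months (5) using a chi-squared test".

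Other sections use the terms in their ordinary sense:

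- Section 2.3, on the earlier virtual trial, reports that "the survivor retention rate was 84%, while the survivor retention rate in traditional ALS trials is 78"%.
- Section 3.3.6, directly after its definition, says: "Our previous virtual trial with Lunasin had a dropout rate of 16% at 12 months (6").
- Section 4.1.2 allows for 15% dropout over 6 months when setting the sample size, plainly meaning participants lost.

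No section corrects the definition in 3.3.6 or 4.1.5.

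**The concern.** A participant who completes the Month 6 Visit has been retained. The percentage who complete is therefore the retention rate, and dropout is 100% minus it. Both places that define the endpoint attach the completion percentage to the name *dropout rate*, and 4.1.5 then sets it beside a benchmark that really is a dropout rate. The two sides of the comparison run in opposite directions.

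Section 4.1.5 is the only stated test of Secondary Hypothesis 6. An analyst who follows the parenthetical definition would find that better retention produces a higher *dropout rate*, further above 22%. The test could not separate good retention from ordinary retention, and its sign would be reversed. A percentage tabulated under the wrong label could also be misread later by someone without the protocol to hand.

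**Working it through.** **Inputs**

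- Benchmark dropout: 22% at 12 months (sections 1.2, 3.3.6, 4.1.5).
- Survivor retention: 84% in the earlier virtual trial, 78% in traditional trials (section 2.3).
- Dropout in the earlier virtual trial: 16% at 12 months (section 3.3.6).
- Enrolment: 50 (section 3.5).
- Assumptions, because 4.1.5 does not state them: all 50 participants are alive at Month 6; 22% is treated as a fixed value; the test is a one-sample chi-squared on 1 degree of freedom without continuity correction, judged at two-sided 0.05.
- Illustrative result: 8 dropouts and 42 completers (16% and 84%). This borrows the earlier trial's 12-month figure. The 15% planning figure in 4.1.2 would be 7.5 of 50, so 7 dropouts is shown as well.

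**Step 1. Reproduce the protocol's own figures.** 100 − 84 = 16 and 100 − 78 = 22. Both dropout figures are exact complements of the retention figures in 2.3. The documents therefore show which sense of dropout the benchmark carries.

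**Step 2. The statistic.** With observed proportion p, benchmark p0 and n = 50:

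chi-squared = (p − p0)² / [p0(1 − p0)/n]

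For p0 = 0.22 the denominator is 0.22 × 0.78 / 50 = 0.003432. It is the same for p0 = 0.78.

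**Step 3. The illustrative result under each reading.**

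- As written, 84% against 22%: 0.62² / 0.003432 = 0.3844 / 0.003432 = 112.0, p about 4 × 10⁻²⁶. Because 84% is above 22%, it reads as far worse dropout.
- Aligned, 16% against 22%: 0.06² / 0.003432 = 0.0036 / 0.003432 = 1.05, p = 0.31.
- Aligned the other way, 84% against 78%: the difference is again 0.06, so the result is again 1.05.

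**Step 4. Does this depend on the example?**

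| Dropouts of 50 | As written: completion v 22% | Aligned: dropout v 22% |
|---|---|---|
| 11 (22%) | 78%: chi-squared 91.4 | 0.00, p = 1.00 |
| 8 (16%) | 84%: chi-squared 112.0 | 1.05, p = 0.31 |
| 7 (14%) | 86%: chi-squared 119.4 | 1.86, p = 0.17 |
| 5 (10%) | 90%: chi-squared 134.7 | 4.20, p = 0.041 |

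The first row is the clearest. Retention exactly equal to that of traditional trials gives 91.4 as written and zero when aligned. The literal test is non-significant only with 6 to 16 completers (12% to 32%), that is, with 34 to 44 of 50 lost. From 17 completers upward it rejects, always in the direction labelled worse.

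**Step 5. What alignment leaves open.** The trial lasts 6 months and the benchmark is at 12. Under an assumed constant hazard, 22% at 12 months corresponds to 1 − √0.78 = 11.7% at 6 months. Five dropouts (10%) give p = 0.041 against 22% but p = 0.71 against 11.7%. This is a different issue from the inverted definition, and correcting the definition does not remove it.

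**The case against.** The best defence is that nobody would carry out the literal test. Section 4.1.5 opens by stating that the aim is to see whether retention is greater. Section 3.3.6 follows its definition with two comparators that are both dropout in the ordinary sense, and 4.1.2 uses the term in that sense too. A chi-squared test works on counts of completers and non-completers; once these are lined up with the benchmark's 78/22 split, the label makes no difference. An 84% dropout reported among people who finished the trial would be noticed at once. The Month 6 completion data are collected either way, so the wording can be put right without loss.

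Most of this stands. A reader might infer from the two sections that the trial is bound to report a meaningless or reversed retention result. The documents do not support that: the intended measure can be recovered from their own figures, and the value 112 arises only on a literal reading with assumed inputs. A reader might also suppose that the slip reaches the primary analysis or the sample size. It does not, since 4.1.2 uses dropout correctly as loss.

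What does not stand is the step from recoverable intent to no correction needed. The inversion is in the operative definitions, not in background text, and it occurs twice. To run the intended test, an analyst must overrule an explicit definition, and can do so in two ways: change the measure or change the benchmark. Changing both, or neither, leaves the comparison misaligned.

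**Conclusion.** The definition of the dropout rate in 3.3.6 and 4.1.5 is the wrong way round, and the comparison in 4.1.5 is wrong as written. On a literal reading, the test of Secondary Hypothesis 6 rejects for almost any plausible result and points the wrong way. In the illustration, chi-squared is 112 as written against 1.05 (p = 0.31) when aligned. Those values rest on 50 living participants, 8 dropouts, and 22% treated as fixed in a one-sample test; the inversion itself rests on none of these.

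The reach is limited to one secondary feasibility endpoint. The primary ALSFRS-R analysis is untouched, and the protocol's own complementary figures show what was meant. A reader might take the aligned p = 0.31 as the sound answer for such a result. It is not: it shows only the effect of the inversion, because the benchmark still covers twice the trial's follow-up.

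**What to change.** Choose one direction and use it in both 3.3.6 and 4.1.5:

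- define the dropout rate as the percentage of living enrolled participants who do **not** complete the Month 6 Visit, and compare it with a dropout benchmark; or
- rename the measure *retention rate*, keep the completion percentage, and compare it with the complement of the benchmark (78%, as in section 2.3).

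The two are arithmetically identical, so the choice is one of presentation. The cost is a change of wording in two sections, with no effect on data collection, staff or participants. The mismatch between 6-month follow-up and the 12-month benchmark needs its own decision; neither rewording settles it.
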